393 Qualitative evaluation

394 The Framework Analysis approach (48) will be used to analyse the data to generate
395 important categories and themes that encapsulate the elements that have influenced the
396 development and implementation of the new programme. Key steps outlined by Gale et al. (2013)
397 will be adopted (49). To begin, we will familiarise ourselves with the data by thoroughly reading
398 the transcript and listening back to the recorded interviews, if necessary. Field notes made during
399 and after the interviews will be read alongside the transcripts to ensure that the context was taken
400 into consideration. Based on the 12 factors outlined used to describe the model and process of care
401 at each of the five sites (Table 3), we will identify overarching categories where codes that are
402 conceptually related will be grouped.

403 A preliminary list of codes was derived from the literature (28, 50-54) as well as from our
404 initial first impressions. Initially, three members of the research team will independently code the
405 same two transcripts, allowing the codes to emerge inductively from the data in this open coding
406 process. Subsequently, the team will compare and discuss the codes, agree on a set of codes, assign
407 code labels, and provide each with a brief definition. This will form the working analytical

408 framework which will be applied to subsequent transcripts using NVivo (Release 1.0) (released in
409 March 2020). Once the data has been coded using the analytical framework, we will group codes
410 that are conceptually similar under the identified categories in a matrix. We will refine and create
411 new categories, if necessary. Key themes will be generated from the codes by reviewing the matrix
412 and making connections within and between categories. This process will be guided by the
413 research objectives and analytical framework as well as new concepts generated inductively from
414 the data. During the interpretation stage, we plan to take the analysis beyond describing the
415 implementation at each site towards developing themes to offer possible explanations for what was
416 happening across sites. The interpretation of findings will be discussed within the team and
417 presented to selected respondents from the implementation sites for member checking.

418 Quantitative evaluation

419 The process indicators will be computed for each month and at quarterly intervals monitor
420 the progress of the programme. Baseline characteristics will be described with mean and SD for
421 continuous variables, and number and percentage for categorical variables.

422 For survey-collected outcomes, Generalised Linear Models (GLM) will be used to allow us
423 to make inferences about the population when accounting for the within-subject correlation.

424 A propensity score conditional upon observed covariates will be computed for all cases
425 (Figure 1). Variables will include sociodemographic information, disease burden measured by the
426 Charlson Comorbidity Index (55), and physical functional status. We will match 2 comparators to
427 1 case using nearest-neighbour matching. In a Monte Carlo simulation, the mean squared error for
428 a 2:1 match was minimised in 84 percent of the simulations compared with 68 percent for a 1:1
429 match (56). Nearest neighbour matching based on a calliper of 0.01 of the standard deviation of
430 the propensity score will be used (46, 57). Only cases and comparators with propensity scores

431 falling within a common support region range will be included in the analysis to ensure
432 comparability of the two groups.

433 In the multivariable regression analysis of count data, Poisson distribution or Negative
434 Binomial distribution (variance greater than the mean) will be used. Negative Binomial regression
435 can be used for over-dispersed count data when the conditional variance exceeds the conditional
436 mean. GLM will be used for modelling non-normally distributed continuous data such as length
437 of stay and healthcare cost. The results will be presented as incidence-rate ratios (IRRs). All
438 analyses will be performed using Stata/SE 16.1(58), with the level of significance set at 5%.

439 Integration of qualitative and quantitative data

440 Qualitative and quantitative data are collected concurrently and analysed separately. In the
441 final interpretation of the data, we will bring together and triangulate the results from the various
442 coordinated parts (59). Findings from each component of a study will be listed to allow the
443 evaluation team to look for convergence in findings, offer complementary information on the same
444 issues and to highlight discrepancies (60). Findings from interviews, focus group discussions and
445 participant observations will be used to contextualise quantitative process indicators and for
446 corroboration. Qualitative findings could offer explanations for the effectiveness of the GSH in
447 terms of the impacts on health status, quality of life, user experience, and healthcare resource use
448 and costs.

449 **Discussion**

450 The purpose of the GSH programme is to provide comprehensive and coordinated care for
451 frail older adults in the community, and the programme aims to achieve this through collaborative
452 working arrangements with various health and social service providers in the community. The
453 suite of services provided includes conducting CGA to identify the needs of older adults, and to

454 increase accessibility of frail older adults to essential services. Five GSH pilot sites share these
455 common goals but due to differences in their innate organisational operations, the design of the
456 GSH model was different to harness their existing relationships and organisational strengths.

457 The motivation to conduct a multiple methods evaluation is driven by the need to provide
458 good quality evidence on the organisation of community-based frailty care. Integration between
459 acute care and other forms of care in the community is becoming increasingly advocated (61). As
460 GSH is a model of care that aims to provide comprehensive care to frail older adults, it is essential
461 to gain rich insights into the development and implementation of the programme. The
462 understanding of underlying mechanisms will help us determine each programme's effects on
463 patients' health outcomes, programme cost-effectiveness, and the programme replicability.
464 Variations in the operations at each site demands that our evaluation methods be rigorous and
465 consistent across all sites. This will enable us to identify essential links in each model and
466 contribute more effectively to the planning of future models that provide comprehensive care.

467 **Strengths and limitations**

468 The study protocol has several strengths. Firstly, the multiple method approach allows in-
469 depth understanding of the programme from the point of view of different stakeholders, as well as
470 the programme's attributed health outcomes and costs impact. Secondly, this approach also
471 enables us to triangulate our findings, and cross compare the validity and reliability of our findings
472 through the different mediums of data collection. Finally, the choice of propensity score to match
473 patients will allow a close match in baseline characteristics between treatment and comparator
474 groups. This method attempts to replicate the balance in characteristics achieved by randomisation,
475 and thereby minimise selection bias. As a result, it contributes to the validity of conclusions to be
476 made on healthcare utilisation and cost outcomes.

477 The research protocol also has several limitations. Firstly, the data collection process will
478 only account for enrollees who agree to receive services delivered by the GSH programme. This
479 inadvertently excludes patients who seek alternative care in other care services in Singapore. As a
480 result, this exclusion might lead to an underestimation of the true treatment effect. Secondly,
481 although we can reduce selection bias through propensity score matching, there might be
482 unmeasured confounders that introduce hidden biases in our analyses.

483 In summary, the GSH aims to provide comprehensive health care services to frail older
484 adults in Singapore. They achieve this by partnering with health and social service providers in the
485 community and aim to increase accessibility and ease transition across different health services.
486 We believe that this evaluation study can provide valuable evidence of the impact and effectiveness
487 of the GSH. Lessons learnt from this study will be disseminated to programme implementers and
488 inform the design of similar programmes nationally.

489

490 **Declarations**

491 **Ethics approval and consent to participate**

492 This protocol describes the proposed evaluation of the Geriatrics Services Hub programme. The
493 described study has received ethical approval from the NHG Domain Specific Review Board
494 (DSRB Ref: 2019/00925).

495 **Consent for publication**

496 Not applicable

497 **Availability of data and materials**

498 Not applicable

499 **Competing interest**

500 The authors declare no conflict of interest with respect to the research, authorship and/or
501 publication of this article.

502 **Funding**

503 This study was funded by the Ministry of Health, Singapore (HSDP Project Number 19X01). The
504 funder has played no role in the study design or preparation of the manuscript.

505 **Authors' Contribution**

506 TWS conceived and designed the study, drafted and revised the article. NZL, THTR, SN, RC,
507 MLG, ET and PHJT designed the study, drafted and revised the article. DYY, WCH and LWS

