275 organisations including primary care clinics, and aged care facilities will be identified for another
276 round of focus group discussions. They may include the heads of doctors, nurses and
277 administrative staff who provided services within the new programme for at least six months.
278 Third, we aim to identify at least ten participants who receive care under the new model for at least
279 three months for the last round of focus group discussions. They must be able to take part in
280 conversation for at least 60 minutes. For individuals who do not have the capacity to participate,
281 his/her primary caregiver is eligible for participation.

282 We will conduct participant observations to better understand the processes involved by
283 shadowing 3 to 5 members of the staff over the course of one week per site to account for day-to-
284 day variations and job role differences.

285 Quantitative Evaluation

286 First, quality indicators will be developed to measure the processes of care for all individuals
287 enrolled into each programme. The relevant sub-populations accessing each care component will
288 form the denominator for computation of the indicators.

289 Second, we aim to recruit patients enrolled in the new programme. A target sample of 300
290 participants per site will be recruited. The sample was calculated based on the Barthel Index (100
291 points) – a scale to assess physical functioning, the key health outcome expected to improve as a
292 result of participation in the GSH. We computed the sample size for each participating site using
293 the dependent t-test to detect a small effect size of 0.2 (based on $\beta = .80$, $\alpha = .05$) (45). The result
294 was a minimum sample size of 156 per participating site. Allowing 20% rejection rate at the first
295 instance and a subsequent attrition rate of 30%, we would need to approach 300 individuals at the
296 first instance.

297 (Insert) Figure 1 Study sample for quantitative evaluation

298 Third, propensity score matching will be used to match programme enrollees and a
299 constructed comparator group. Both groups will be matched based on their probability of being
300 enrolled into the programme conditional on baseline covariates (46). The propensity score can be
301 used to mitigate selection bias in a non-randomised study. All programme enrollees will be
302 included as cases. Data on comparators will be derived from a Ministry of Health dataset

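### The sample-size statement prints beta = .80 where the value used was evidently power = .80, and 156 per site gives that power only with a one-sided 5% test

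*Combined protocol and SAP*

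**What the plan says.** The survey sample size is set out in the Combined protocol and SAP, under Methods, Study Sample, Quantitative Evaluation.

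- **Outcome.** "The sample was calculated based on the Barthel Index (100" points), described as the key health outcome expected to improve. No standard deviation or raw change is given, only a standardised effect.
- **Test, effect and error rates.** "the dependent t-test to detect a small effect size of 0.2 (based on $\beta = .80$, $\alpha = .05$) (45", where 45 is a reference number. Beta is not defined, and alpha is not said to be one-sided or two-sided.
- **Result.** The result "was a minimum sample size of 156 per participating site".
- **Inflation.** "Allowing 20% rejection rate at the first" "instance and a subsequent attrition rate of 30%, we would need to approach 300 individuals at the" first instance.

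Under Data Analysis, Quantitative evaluation, all analyses are to be run "with the level of significance set at 5" per cent, again without sidedness. No other place in the document gives a power figure or says that beta is used to mean power.

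**The concern.** In a sample-size statement, beta printed next to alpha is the type II error, and power is 1 - beta. Taken at its word, the paragraph describes a design with 20% power, and the number of patients printed in the next sentence does not follow from that input. A sample-size paragraph should be reproducible from its own inputs, and this one is not.

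What is at stake is modest but practical. Outcomes are to be compared for each programme separately (Table 2), so someone will have to interpret a null Barthel result at a single site and will look here for the planned chance of missing the target effect. The natural repair is to read .80 as power and beta as .20. That repair is right only if the 5% test is one-sided, which the document does not say. So the realistic doubt is whether the planned miss rate at 156 is 20% or about 30%.

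**Working it through.** **Inputs** (all from the sample-size paragraph): paired t-test; standardised effect d = 0.2; alpha = .05, sidedness not stated; printed beta = .80; printed n = 156.

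**Method.** Exact power of a paired t-test with n pairs comes from the noncentral t distribution with n - 1 degrees of freedom and noncentrality d × √n. The smallest n reaching the required power is then found. As a cross-check, the normal approximation is n = ((z_alpha + z_power) / d)², rounded up.

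**Step 1: reproduce 156.** Take one-sided alpha .05 and power .80.

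- Normal approximation: ((1.645 + 0.842) / 0.2)² = 12.435² = 154.6, so 155.
- Exact t: power is 0.798 at n = 155 and 0.8002 at n = 156, so the minimum is 156.

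The printed figure is reproduced exactly.

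**Step 2: take beta = .80 literally (power .20, z = -0.842).**

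- One-sided: ((1.645 - 0.842) / 0.2)² = 16.1, so 17; exact t gives 18.
- Two-sided: ((1.960 - 0.842) / 0.2)² = 31.2, so 32; exact t gives 33.

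Neither is near 156.

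**Step 3: power .80 with a two-sided test.** ((1.960 + 0.842) / 0.2)² = 196.3, so 197; exact t gives 199. This does not reproduce 156 either.

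**Minimum pairs, exact t:**

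| 5% test | Power .20 (beta .80) | Power .80 (beta .20) |
|---|---|---|
| One-sided | 18 | **156** |
| Two-sided | 33 | 199 |

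**Step 4: what 156 delivers.**

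| 5% test | Power at n = 156 | Beta at n = 156 |
|---|---|---|
| One-sided | 0.8002 | 0.20 |
| Two-sided | 0.699 | 0.30 |

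Of the four combinations tried, only one-sided alpha .05 with power .80 yields 156. Under neither sidedness is beta at 156 anywhere near .80.

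**Step 5: the inflated numbers.** 156 / 0.7 / 0.8 = 278.6, so 279, and 300 to approach is a rounding up. If 300 are approached, 300 × 0.8 × 0.7 = 168 complete, with power 0.826 one-sided or 0.732 two-sided. The same paragraph also gives 300 as the number to be recruited. On that reading 300 × 0.7 = 210 complete, with power 0.893 one-sided or 0.823 two-sided. Correcting the symbol moves none of these counts.

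**The case against.** The strongest reply is that this is a slip of notation that any statistician will see through. The value .80 sits beside alpha = .05, the next sentence gives 156, and 156 is what power .80 yields. No sum is wrong, and no planned quantity (156, 300, alpha or the effect size) changes when the symbol is corrected. Nor is 156 the number likely to be analysed, since the allowance for refusal and attrition leaves somewhat more. All of that stands, and it is why the point is of low severity.

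A reader might infer from the printed beta that each site was designed to miss the target effect 80% of the time. The document does not support that: a design with 20% power would have asked for 18 or 33 pairs, and no sidedness gives beta = .80 at 156. For the same reason, it would be misleading to present the gap between .80 and the true beta as a quantitative shortfall in the design. It is a mix-up of symbols.

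The reply does not dispose of the point entirely. The intended meaning can be recovered only by back-calculation, and that calculation works only with a one-sided test that the document never states. A reader who simply substitutes 80% power will be about 10 percentage points too high at 156 if the 5% test is two-sided.

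**Conclusion.** The stated error rate is wrong as written, in a narrow sense: power of .80 has been printed as beta. The accompanying 156 has power .80 and beta .20 only for a one-sided 5% paired t-test. For a two-sided 5% test, power at 156 is about .70, beta is about .30, and 80% power would need 199, which is 43 more pairs than the plan prints (199 - 156).

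Two further inferences should be resisted. One is that beta at 156 is simply .20, which depends on a sidedness the document leaves open. The other is that the study is shown to be undersized and must enrol more patients. The document does not say that the test is two-sided, and restating the power and sidedness correctly changes no count.

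These figures rest on the paired t-test and the standardised effect of 0.2 named in the sample-size paragraph. They do not describe the power of the generalised linear model planned for the survey outcomes, for which the document gives no calculation. Severity is low: a stated figure needs correcting, and nothing in the conduct of the study does.

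**What to change.** In the sample-size paragraph, replace the beta = .80 entry with the power and the sidedness that belong to 156. Use whichever of these matches the intended analysis:

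- power = .80 (beta = .20), one-sided alpha = .05; or
- power about .70 (beta about .30), two-sided alpha = .05.

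Then add the same sidedness to the 5% significance level in the Data Analysis section, so that the two places agree. Changing the symbol to power = .80 without stating sidedness would leave a statement that is false for 156 if the test is two-sided.

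The cost is one phrase in the sample-size paragraph and one or two words in Data Analysis. No change to enrolment, follow-up or data collection is required.

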To assess the process of development and implementation of the new programme	
• To examine the perceptions, roles, responsibilities, and experience in developing and implementing each programme• To understand the workflow from the perspective of each profession for each of the new programmes• To improve competency of primary care providers in identifying, caring and managing geriatric patients in the community• To explore differences in contextual factors across the five sites that have influenced implementation experiences and outcomes• To understand care recipients' experiences in receiving frailty care in the community	Qualitative - Semi-structured in-depth interview with key policy and programme decision-makers Qualitative - Semi-structured focus group discussions with health and social care professionals and care recipients Qualitative – Participant observations Quantitative – Longitudinal monitoring of process indicators
To assess the health, quality of life, and user experience effects on care recipients and the burden of care on primary caregivers	
• To compare outcomes between baseline, 3- and 6-months for each programme	Quantitative - Pre-test post-test design using survey-based data collection
To determine the impact on healthcare utilisation and cost impact of the new programme	
• To assess the use of healthcare services and costs between participants and non-participants for each programme	Quantitative - Retrospective cohort design with propensity score matched comparators

208
209 Based on the components the sites are funded for (Table 1), we will evaluate the GSH
210 program conducted by Ng Teng Fong General Hospital (NTFGH) based on evaluation objective 1
211 – to assess the process of development and implementation of the new programme. The focus is
212 on competency building, with the funding being utilised to cover the time spent by trainers and
213 trainees. In addition, the funding will not be used to cover healthcare costs incurred by patients.

214 Based on these considerations, evaluation objectives 2 and 3 would not be representative of the
215 results of the program. The remaining four sites will be evaluated on all three evaluation objectives
216 as their funding structures includes subsidising the healthcare costs of patients.

217 **Qualitative Evaluation**

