- 354 1. GSH sites offer a range of medical, social and other services through either direct provision
355 or referrals. Given that the model is intended to bridge service gaps (conduct of CGA in
356 the community), in the short-term, we hypothesis **an increase in the utilisation of**
357 **appropriate services** (rehabilitation, ambulatory services) in this time-limited programme.
- 358 2. GSH participants are expected to benefit from the comprehensive package of health and
359 social services and multidisciplinary team approach. With **better care coordination and**
360 **improved access**, it is likely to elicit a **higher level of satisfaction** relative to comparator
361 groups.
- 362 3. Education of the client about self-care and making decisions about potential care options
363 with inputs from a multidisciplinary team is expected to result in **higher level of shared**
364 **decision making** and **engagement** relative to comparator groups.
- 365 4. It is hypothesised to result in **better functional status and health outcomes**, **might reduce**
366 **the healthcare utilisation** (emergency hospitalisation, nursing home admission),
367 **caregiver burden** and **the associated indirect cost**. In turn, we might expect **overall costs**
368 **to be lower** compared to the comparison group.

369 An interviewer-administered survey will be conducted to collect data on demographic and

370 baseline health status, and data measuring the impact of the programme on patient activation, user

371 experience and satisfaction with care, health status, quality of life, the burden of care on primary

372 caregivers, and health utilisation and cost. The data are collected at baseline, 3-months and 6-

373 months (Table 5). After obtaining informed consent, participants will be asked to complete a

374 survey estimated to take about 45 to 90 minutes. Participants will complete the survey up to three

375 time-points – baseline (within 1 month of programme enrollment) and at 3-months and 6-months.
376 The primary caregiver will also be asked to complete a 5 to 10-minute survey at the same three
377 time points on caregiver burden. In the event a participant is clinically certified to have dementia,
378 we will allow a proxy respondent to answer on behalf of the main participant. Participants will
379 receive a token of appreciation for their involvement in the study.

380 Table 5. List of indicators for measuring programme impacts

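### The per-site minimum of 156 fits a one-sided test that the plan never declares, and 300 is given both as the number recruited and as the number approached

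*Combined protocol and SAP*

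**What the plan says.** The sizing of the survey cohort is in Methods, Study Sample, Quantitative Evaluation. It is based on the Barthel Index, described as "the key health outcome expected to improve as a" result of taking part. For each site the plan used "the dependent t-test to detect a small effect size of 0.2", with beta given as .80 and alpha as .05, and reports that the result "was a minimum sample size of 156 per participating site".

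The figure of 300 appears twice in that paragraph. First, a target of 300 "participants per site will be recruited". Then, after a 20% refusal rate: "instance and a subsequent attrition rate of 30%, we would need to approach 300 individuals at the" outset.

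Elsewhere:

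- Table 2 states the survey objective as "To compare outcomes between baseline, 3- and 6-months for each programme".
- Hypothesis 4 under Study Procedure expects "better functional status and health outcomes".
- Evaluation Design restricts this objective to four sites: "The remaining four sites will be evaluated on all three evaluation objectives".
- Data Analysis, Quantitative evaluation, sets an unqualified 5% significance level and plans generalised linear models for the survey outcomes.

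The text nowhere says one-sided or two-sided, and nowhere says which standard deviation the 0.2 is scaled to.

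**The concern.** A reader who takes alpha .05 in the usual two-sided sense and 0.2 as the standardised change cannot reproduce 156. The reader also cannot tell from the text how many completers to expect, because recruiting 300 and approaching 300 are different things once 20% refuse.

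Results are to be compared within each programme, so power at the single site governs how a null Barthel result at that site is read. If the analysis is two-sided and 300 is the number approached, the 80% in the plan is not the power the study has. Leaving the sidedness open also allows it to be settled after the data are seen.

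**Working it through.** **Inputs.** All are from the Study Sample section: paired t-test, effect 0.2, alpha 0.05, power 0.80, 20% refusal, 30% attrition, 300 per site. The plan prints beta = .80. Taken literally that is 20% power, which would need only 18 (one-sided) or 33 (two-sided) completers, so power = .80 must be meant.

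**Assumption.** 0.2 is dz, the mean change divided by the SD of change.

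**Formula.** Exact paired t-test power with n completers: a noncentral t distribution with n − 1 degrees of freedom and noncentrality dz·√n, compared with the critical value at 0.05 (one-sided) or 0.025 in each tail (two-sided).

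**Step 1: reproduce the plan's figure.**

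- One-sided 5%: n = 155 gives 0.7979 and n = 156 gives 0.8002. The minimum is 156, which matches the plan.
- Two-sided 5%: n = 198 gives 0.7997 and n = 199 gives 0.8017. The minimum is 199. Two-sided power at 156 is 0.699.

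**Step 2: what 300 means.**

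- The plan's own inflation is 156 / (0.8 × 0.7) = 278.6, which 300 covers. The derivation is therefore for 300 approached.
- 300 approached: 300 × 0.8 = 240 recruited, and 240 × 0.7 = 168 completers.
- 300 recruited: 300 × 0.7 = 210 completers.
- Over the four sites this is 4 × 168 = 672 against 4 × 210 = 840, a difference of 168.

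**Step 3: power under each combination.**

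| Meaning of 300 | Completers per site | One-sided 5% | Two-sided 5% | Change detectable at 80%, two-sided |
|---|---|---|---|---|
| Approached | 168 | 0.826 | 0.732 | 0.217 |
| Recruited | 210 | 0.893 | 0.823 | 0.194 |

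**Step 4: sensitivity to the definition of 0.2.** Suppose 0.2 is scaled instead to the SD of the outcome, with equal SDs and pre-post correlation r. Then dz = 0.2 / √(2(1 − r)). The documents give no r, so the values below are assumptions.

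| r | Two-sided minimum n |
|---|---|
| 0.4 | 238 |
| 0.5 | 199 |
| 0.6 | 159 |
| 0.7 | 120 |

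At r of about 0.608, dz = 0.2 / √0.784 = 0.226 and a two-sided test also gives 156.

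**The case against.** The strongest reply is that nothing has been miscalculated. 156 is exactly right for a one-sided 5% test, 168 completers exceed it, and the plan's language about the Barthel Index is directional. Three of the four combinations reach 80%. The shortfall needs a two-sided test, which the plan does not state, together with the approached reading and 0.2 as the standardised change. With the other scaling and r near 0.608, 156 would even be a correct two-sided number. Figure 1, which follows the calculation, is not reproduced in the text available for this review and may show the flow of participants. The planned analysis is also a model over three time points, not a paired t-test.

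Much of this stands as a limit on the claim. One-sided intent is possible, the scaling is open, and the power figures describe the sizing test only.

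It does not remove the problem. Expecting improvement is not the same as declaring a one-sided test, and neither Table 2 nor Data Analysis declares one. An assumed correlation that could rescue 156 is not stated. Whatever the figure shows, the paragraph still gives 300 two incompatible meanings. The four-site totals bear on expected numbers, not on power, because the sizing is per site.

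**Conclusion.** The concern holds. Three things are certain from the text: the sidedness is undeclared, the 0.2 is undefined, and 300 is both the number recruited and the number approached. The beta notation is also a slip.

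The size of any power loss is conditional. With 0.2 as mean change over SD of change, 156 is the one-sided minimum and the two-sided minimum is 199, which is 43 more completers per site. Two-sided power is 73% if 300 are approached and 82% if 300 are recruited. The one combination below 80% joins the conventional reading of a 5% level, which is a convention and not a statement in the plan, to the plan's own derivation of 300. That the authors ran a one-sided calculation is a strong inference from the exact match, not proof. The point should be fixed, but it does not invalidate the study.

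**What to change.** Rewrite the sample-size paragraph:

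1. **State the sidedness.** Two-sided 5% is the natural default. Suggested wording: *With a two-sided 5% dependent t-test, a standardised mean change (mean change / SD of change) of 0.2 and power = .80, at least 199 completers per site are needed.* If one-sided was intended, keep 156, label it one-sided 5%, and specify the same one-sided test in Data Analysis.
2. **Define the 0.2.** If it is scaled to the outcome SD, give the assumed correlation.
3. **Choose one meaning for 300 and state its consequence.** For a two-sided test, either 300 recruited, 210 completers and 82% power; or 300 approached, 168 completers and 73% power, with a detectable change of 0.217. In the second case say plainly that the expected 168 falls short of 199, and do not claim 80%.
4. **Replace beta = .80 with power = .80.**
5. **Add that these figures apply to the paired t-test**, not to the planned model over three time points.

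The cost is one paragraph and no additional patients. Its only price is candour: under the two-sided, approached reading, the stated power drops from 80% to 73%. Keeping 80% under that reading would instead mean approaching 199 / (0.8 × 0.7) = 355.4, or about 356 people per site. Restating the power avoids that.
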